2.8 Safety analyses

For all safety analyses, the safety set will be used.

Safety summaries (tables, figures) include only data from the on-treatment period with the exception of baseline data, which will also be summarized where appropriate (e.g. laboratory shift tables). In particular, summary tables for adverse events (AEs) will summarize only on-treatment events, with start date during the on-treatment period (treatment-emergent AEs).

The overall observation period will be divided into three mutually exclusive segments:

- **Pre-treatment period:** from day of subject's informed consent to the day before first administration of study treatment
- **On-treatment period:** from day of first dose of study treatment to last dose of study treatment and up to 30 days after last administration of study treatment.
- **Post-treatment period:** starting at day 31 after last administration of study treatment (MBG453 or HMA).

Overall safety period: from date of first administration of study treatment to 30 days after the date of the last administration of HMA or 150 days after the last dose of MBG453 whichever is later.

2.8.1 Adverse events (AEs)

All information obtained on adverse events will be listed.

Treatment emergent adverse event (TEAE) defined as any adverse event which started on or after the day of first dose of study treatment and before 30 days after last dose of study treatment.

Summary tables for adverse events (AEs) will include only AEs that started or worsened during the on-treatment period. The number (and percentage) of subjects with treatment emergent AEs will be summarized by primary system organ class, preferred term and maximum severity (based on CTCAE grades).

AEs will be summarized by number and percentage of subjects having at least one AE, having at least one AE in each primary system organ class (SOC) and for each preferred term (PT). A subject with multiple occurrences of an AE will be counted only once in the respective AE category. A subject with multiple CTCAE grades for the same preferred term will be summarized under the maximum CTCAE grade recorded for the event. AEs will be assessed according to the Common Terminology Criteria for Adverse Events (CTCAE) version.

All AEs reported in the AE eCRF page will be listed along with the information collected on those AEs, e.g. toxicity grade, relationship to study treatment, outcome, action taken etc. AEs

that started during the pre-treatment, on-treatment, post-treatment and after the overall safety period will be flagged.

Separate summaries will be provided for study treatment related adverse events, death, serious adverse events, non-serious adverse events, adverse events leading to treatment discontinuation, and adverse events leading to dose adjustment by primary system organ class and preferred term.

Selected summaries of adverse events will be produced for the overall safety period. All deaths (on-treatment and post-treatment) will be summarized.

All AEs, deaths, and serious adverse events (including those from the pre- and post-treatment periods) will be listed and those collected during the pre-treatment, post-treatment and overall safety period will be flagged. Subjects who are having AE after transplantation or antineoplastic therapies will be listed & flagged.

In the AE summaries, the primary system organ class will be presented alphabetically, and the preferred terms will be sorted within primary SOC in descending frequency. The sort order for the preferred term will be based on their frequency in the MBG453 + HMA arm. The summaries will show ‘All grades’ (including AEs with missing grade) and ‘Grades ≥ 3 ’.

The following adverse event summaries will be produced selecting all or a subset of AEs depending on seriousness, relationship to study treatment, outcome or action taken:

- AEs (all AEs by SOC and by PT) and separately those considered related to study treatment and all AEs by HMA
- SAEs and separately those considered related to study treatment
- SAEs with number of occurrences (an occurrence is defined as >1 day between start and prior end date of record of same preferred term).
- Non-SAEs
- SAEs with fatal outcome and separately those considered related to study treatment
- AEs leading to study treatment or MBG453/HMA discontinuation and by HMA
- Related to study treatment AEs leading to study treatment discontinuation
- AEs leading to dose adjustment/interruption for (MBG453/HMA) and study treatment
- AEs requiring additional therapy
- COVID-19 related adverse events by MedDRA COVID-19 (SMQ) terms.

AEs will be summarized by number and percentage of subjects having at least one AE, having at least one AE in each primary system organ class (SOC) and for each preferred term (PT). A subject with multiple occurrences of an AE will be counted only once in the respective AE category. A subject with multiple CTCAE grades for the same preferred term will be summarized under the maximum CTCAE grade recorded for the event. AEs will be assessed according to the Common Terminology Criteria for Adverse Events (CTCAE) version 5.0.

In addition, all AEs and SAE by SOC and PT will be also provided on the overall safety period.

Adverse events for safety follow up period (day 31-150 after last dose of study drug) will be described by system organ class and preferred term.

For the legal requirements of ClinicalTrials.gov, two required tables on <on-treatment/treatment emergent> adverse events which are not serious adverse events with an incidence greater than X% and on <on-treatment/treatment emergent> serious adverse events and SAE suspected to be related to study treatment will be provided by system organ class and preferred term on the safety set population.

If for a same patient, several consecutive AEs (irrespective of study treatment causality, seriousness and severity) occurred with the same SOC and PT:

- A single occurrence will be counted if there is ≤ 1 day gap between the end date of the preceding AE and the start date of the consecutive AE
- More than one occurrence will be counted if there is > 1 day gap between the end date of the preceding AE and the start date of the consecutive AE

For occurrence, the presence of at least one SAE / SAE suspected to be related to study treatment / non-SAE has to be checked in a block e.g., among AE's in a ≤ 1 day gap block, if at least one SAE is occurring, then one occurrence is calculated for that SAE.

The number of deaths resulting from SAEs suspected to be related to study treatment and SAEs irrespective of study treatment relationship will be provided by SOC and PT."

2.8.1.1 Adverse events of special interest / grouping of AEs

An adverse event of special interest is a grouping of adverse events that are of scientific and medical concern specific to compound MBG453. These groupings are defined using MedDRA terms, SMQs (standardized MedDRA queries), HGLTs (high level group terms), HLT (high level terms) and PTs (preferred terms). Customized SMQs (Novartis MedDRA queries, NMQ) may also be used. A NMQ is a customized group of search terms which defines a medical concept for which there is no official SMQ available or the available SMQ does not completely fit the need. It may include a combination of single terms and/or an existing SMQ, narrow or broad. These searches will be defined in the eCRS (electronic Case Retrieval Strategy) in the DMS (Document Management System) and a listing of search terms will be provided in the CSR.

For each specified AESI, number and percentage of subjects with at least one event of the AESI occurring during on treatment period will be summarized together with the individual preferred terms in that grouping. In addition, number and percentage of subjects with at least one AESIs by maximum CTC grade, related AESIs, serious AESIs as well as action taken and outcome of the respective AESI will be summarized.

Of note, AESI will be included only in the final CSR.

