- Drug interrupted/withdrawn

6. its outcome (i.e. recovery status or whether it was fatal)

If the event worsens the event should be reported a second time in the CRF noting the start date when the event worsens in toxicity.

Once an adverse event is detected, it must be followed until its resolution or until it is judged to be permanent (e.g. Continuing at the end of the study), and assessment must be made at each visit (or more frequently, if necessary) of any changes in severity, the suspected relationship to the interventions required to treat it, and the outcome.

Conditions that were already present at the time of informed consent should be recorded in medical history of the participant.

Adverse events (including lab abnormalities that constitute AEs) should be described using a diagnosis whenever possible, rather than individual underlying signs and symptoms. When a clear diagnosis cannot be identified, each sign or symptom should be reported as a separate adverse event.

Adverse event monitoring should be continued for at least:

- 30 days following the last dose of azacitidine or decitabine or INQOVI (oral decitabine), or 150 days following the last dose of MBG453 (sabatolimab), whichever is later (After the safety follow-up on site visit on Day 30, participants will be followed via telephone call for the Day 90 and Day 150 (or onsite visit if patient happens to be visiting the site)).

OR

- Until the start of a new post treatment antineoplastic medication if sooner than the 150 days mentioned above. If a patient starts post treatment antineoplastic medication, then only adverse events suspected to be related to study treatment should be collected, up to 150 days after discontinuation of MBG453 (sabatolimab).

Adverse events separate from the progression of malignancy (i.e. deep vein thrombosis at the time of progression or hemoptysis concurrent with finding of disease progression) will be reported as per usual guidelines used for such events with proper attribution regarding relatedness to the drug. Information about adverse drug reactions for the investigational drug can be found in the Investigator's Brochure (IB).

Abnormal laboratory values or test results constitute adverse events only if they fulfill at least one of the following criteria:

- they induce clinical signs or symptoms
- they are considered clinically significant
- they require therapy

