5.4 Date of last administration of study treatment (combination)

The date of last administration of study treatment (or end date of study treatment) is defined as the last date when the last non-zero dose of any last component of the study treatment (MBG453 (sabatolimab) in combination with HMAs (IV/SC/Oral)) is administered.

5.5 Date of last exposure to HMA and investigational drug and date of last exposure to study treatment (combination)

One planned cycle length is 28 days. HMA drugs are planned to be administered every cycle between Day 1 and Day 9 with different schedules. MGB453 is administered every 4 weeks, on Day 8 out of a 28 days cycle, unless there was a toxicity leading to a dosing interval increase.

As treatment is given in cycles, the date of last administration of study treatment is not considered the date of last exposure but instead the planned end date of the last cycle in which the last non-zero dose was given.

The **date of last exposure to MBG453** is therefore calculated as:

- Minimum (last date of administration of investigational drug + 27 days, date of death, last contact date in case subject is lost to follow-up), as MBG453 injections is given Q4W (in case of change to Q8W, the cycle would end after 55 days)

The **date of last exposure to HMA** drugs is calculated as:

The date of last exposure to azacitidine

- Minimum (last date of administration of azacitidine + 20 days, date of death, last contact date in case subject is lost to follow-up) as azacitidine is given daily every cycle during

7 days at the beginning of each cycle (between Day 1 to Day 9) (total cycle length 28 days).

The date of last exposure to decitabine

- Minimum (last date of administration of decitabine + 22 days, date of death, last contact date in case subject is lost to follow-up) as decitabine is given daily every cycle during 5 days at the beginning of each cycle (between Day 1 to Day 5) (total cycle length 28 days).

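### AESI summaries stop 30 days after the last dose of any study drug, so no specified table groups the AESIs that start later in the 150-day collection period

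*SAP*

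**What the plan says.** **AESI summaries.** SAP 2.8.1.1 provides that, for each AESI, the "number and percentage of subjects with at least one event of the AESI occurring during on treatment period will be summarized" with its preferred terms. A second sentence adds maximum grade, related and serious AESIs, action taken and outcome. It names no period, so the general rule in SAP 2.8 applies: "Safety summaries (tables, figures) include only data from the on-treatment period with the exception of baseline data".

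**On-treatment period.** SAP 2.8 defines it as running "from day of first dose of study treatment to last dose of study treatment and up to 30 days after last administration of study treatment". SAP 2.1.1.4 takes the last administration of study treatment to be the last non-zero dose of any component.

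**Collection and overall safety period.** Protocol 10.1.1 keeps AE monitoring open for 30 days after the last HMA dose or "150 days following the last dose of MBG453 (sabatolimab), whichever is later". SAP 2.8 mirrors this: "Overall safety period: from date of first administration of study treatment to 30 days after the date of the last administration of HMA". The sabatolimab limit of 150 days applies instead where it falls later.

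**What is tabulated beyond day 30.** SAP 2.8.1 gives all AEs and SAEs by system organ class (SOC) and preferred term (PT) for the overall safety period, and AEs by SOC and PT for days 31–150. It also promises an unspecified selection of AE summaries for the overall period. AE summaries show all grades and Grade 3 or higher. Listings carry grade, relationship, outcome and action, with the period flagged. None of these provisions names AESIs.

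**The concern.** Safety is the primary objective. AESIs are the groupings that the sponsor singled out as specific to sabatolimab, and Protocol 4.5 describes immune-related events as an anticipated risk of the class. The SAP runs its general AE and SAE tables on both the on-treatment and the overall periods, but specifies the AESI tables for the on-treatment period only, and gives no reason.

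The SOC/PT tables do not fill the gap. An AESI can be built from standardised or customised MedDRA queries, high-level terms and PTs. A participant counts once under each PT, so someone with two PTs in one AESI group appears twice, and PT rows cannot be added to give the number of participants with that AESI. Nor do these tables give the group's maximum grade, relatedness, action or outcome. A reader who goes to the AESI tables for the compound-specific risk sees only part of the period in which such events were collected.

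**Working it through.** **1. The plan's own window.** On-treatment ends at last dose + 30 days and collection ends at last sabatolimab dose + 150 days. The difference is days 31–150, the follow-up window named in SAP 2.8.1. Its length is 150 − 30 = 120 days, and 120/150 = 80% of post-dose days. This is the case in which sabatolimab is the last drug given.

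**2. Effect of continued HMA.** The clock runs from the last dose of any component, so continued HMA extends the window. Inputs: 28-day cycles; sabatolimab on day 8; last HMA day *d* = 5 (decitabine, IV or oral), 7 or 9 (the two azacitidine schedules). These are in Protocol 6.1. Let *k* be the number of HMA cycles given after the last sabatolimab cycle. Counting from the last sabatolimab dose:

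- end of on-treatment period: E = max(0, 28k + d − 8) + 30
- days outside the AESI tables: U = max(0, 150 − E)

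Example, k = 1, d = 5: 28 + 5 − 8 = 25; E = 25 + 30 = 55; U = 150 − 55 = 95.

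| k | U, d = 5 | U, d = 7 | U, d = 9 |
|---|---|---|---|
| 0 | 120 | 120 | 119 |
| 1 | 95 | 93 | 91 |
| 2 | 67 | 65 | 63 |
| 3 | 39 | 37 | 35 |
| 4 | 11 | 9 | 7 |
| 5 | 0 | 0 | 0 |

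With IV or SC HMA, sabatolimab may be given as early as day 5. That puts 5 in place of 8 in the formula and lowers a non-zero U by at most 3 days.

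**3. The eight-weekly schedule.** SAP 5.5 notes that "in case of change to Q8W, the cycle would end after 55 days". If no HMA follows the last sabatolimab dose, the AESI window closes at about day 30, inside that interval. One further HMA cycle takes E to 55, 57 or 59 (d = 5, 7, 9), at or beyond its end. The cut-off therefore falls inside the SAP's own exposure interval only if HMA has also stopped.

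**4. Share of post-dose AESIs affected.** The documents give no onset distribution, so this is an assumption shown as a range, for the case where both drugs stop together. With uniform onset over 150 days the share starting after day 30 is 120/150 = 80%. With onset decaying at half-life h, S(t) = 0.5^(t/h) and the share is (S(30) − S(150)) / (1 − S(150)). For h = 30 this is (0.5 − 0.03125)/(1 − 0.03125) = 48%. For h = 15, 60 and 90 days it is 25%, 64% and 70%.

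**5. Scale.** One participant whose only AESI starts after the window is 1/39 = 2.6 percentage points of AESI incidence. This is the value of one event, not a forecast. For someone treated for 12 months, the worst-case 120 days are 120/(365 + 150) = 23% of all safety days.

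**The case against.** The strongest reply is that nothing is lost. Late events are tabulated by SOC and PT with all-grade and Grade 3 or higher columns, SAEs are tabulated for the overall period, and each event is listed with grade, relationship, outcome and action. SAP 2.8.1.1 also puts the AESI search terms in the CSR, so with 39 participants a reader could rebuild the counts by hand. All of this stands. It confines the point to the grouped AESI summaries, and it rules out the reading that late events vanish from the report.

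The 30-day window also follows the protocol: Protocol 12.5.2 uses the same on-treatment period and limits AE summary tables to it. The two documents therefore do not conflict. There is a reason to keep the periods apart, too. After the day 30 visit, contact is by telephone at days 90 and 150 unless the participant happens to attend, and once new antineoplastic therapy starts only AEs suspected to be related are collected (Protocol 10.1.1). That supports showing the periods separately, but does not explain having no AESI table for the longer one.

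Finally, the promised selection of overall-period summaries, or the separate document for tables, figures and listings, might include an AESI table. The SAP does not rule this out, but it does not commit to it either.

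**Conclusion.** The point holds as a gap in the specified tables. AESIs that start after the on-treatment window have no specified summary of participant-level incidence by AESI group, or of the group's maximum grade, relatedness, seriousness, action or outcome. The gap is about 120 of 150 post-dose days when both drugs stop in the same cycle, and it falls to zero after about five further HMA cycles. These figures assume 28-day cycles and nominal dosing days.

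A reader might infer three stronger things that the documents do not support:

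- **That AESI incidence is understated.** An on-treatment rate labelled as such is not biased. Whether late events exist, and how many, is unknown.
- **That the missing events are immune-related.** This is likely from the stated class risk, but the SAP leaves the AESI terms to the electronic case retrieval strategy and does not list them.
- **That 80% is typical, or that the eight-weekly schedule always puts the cut-off inside an exposure interval.** Both depend on HMA having stopped as well.

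The change is worth making because safety is the primary objective and the remedy is simple. It does not put the on-treatment results in doubt.

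**What to change.** In SAP 2.8.1.1, keep the on-treatment AESI tables and commit to the same summaries (incidence, maximum grade, related, serious, action, outcome) for the overall safety period already defined in SAP 2.8. Count each participant once per AESI group. Show the two periods separately. Add a footnote that ascertainment on days 31–150 is thinner, because contact is mainly by telephone and only suspected-related AEs are collected after new antineoplastic therapy.

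The cost is a few extra tables from existing shells, using a period that the SAP already applies to its AE and SAE tables. Overall-period AESI incidence may be higher than the on-treatment figure, and the report should say why the two differ. No hypothesis is tested, so no error rate is affected. Because the current SAP addendum is itself dated after database lock, the new tables should be labelled as added after lock.

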2.8.2 Deaths

Separate summaries for on-treatment and all deaths (including post-treatment deaths not in the AE CRF but in the survival CRF) will be produced showing deaths reasons by SOC and preferred term.

All deaths (including those from the pre- and post-treatment periods) will be listed and those collected during the pre-treatment, post-treatment and overall safety period will be flagged. A separate listing of deaths prior to starting treatment will be provided for all screened subjects.

2.8.3 Laboratory data

Grading of laboratory values will be assigned programmatically as per NCI CTCAE version 5.0. The calculation of CTCAE grades will be based on the observed laboratory values only, clinical assessments will not be taken into account. CTCAE Grade 0 will be assigned for all non-missing values not graded as 1 or higher. Grade 5 will not be used.

For laboratory tests where grades are not defined by CTCAE v5, results will be categorized as low/normal/high classifications based on laboratory normal ranges.

The following summaries will be generated separately for hematology and biochemistry tests:

For laboratory tests where grades are defined by CTCAE v5.

- Worst post-baseline CTCAE grade (regardless of the baseline status). Each subject will be counted only once for the worst grade observed post-baseline.
- Shift tables to compare baseline CTCAE grades to the worst on-treatment grade.

We will be plan two shift tables (i) One for up to end of core treatment period and (ii) another from Day 1 to end of extension period.

For laboratory tests where grades are not defined by CTCAE v5

- Shift tables using the low/normal/high/low and high classification to compare baseline to the worst on-treatment value.

Listing of all laboratory data with values flagged to show the corresponding CTCAE v5 grades.

If applicable and the classifications relative to the laboratory normal ranges will be presented.

Data summaries will be provided in SI units. The summary of laboratory evaluations will be presented for three groups of laboratory tests: Hematology, Chemistry and Urinalysis. On presenting summary statistics, laboratory data will be grouped and displayed in an alphabetical order within the Hematology and Chemistry groups.

All laboratory data will be listed by subject and visit. If normal ranges are available, abnormalities will be flagged.

2.8.4 Other safety data

2.8.4.1 ECG and cardiac imaging data

No ECG data collected in eCRF only collected in source, if clinically significant ECG findings is recorded on the CRF as either medical history, current medical conditions or adverse events as appropriate.

2.8.4.1.1 Cardiac Imaging Data

No cardiac imaging data collected. Hence Not applicable

2.10 Interim analysis

An interim analysis was performed after all subjects who have completed 6 months follow-up from enrollment (cycle 1 day 1) or discontinued earlier for publication purpose.

Final Analysis will be performed when all subjects complete the core and extension phase and safety follow-up or discontinued early. A final CSR will be written.

3 Sample size calculation

This is an open label, non-randomized, single-arm combination study to assess safety and efficacy of MBG453 (sabatolimab) given with HMAs of investigator's choice (IV/ SC/ Oral). The primary objective of the study is to assess safety profile of this combination drug by 12 months.

Given the above expected incidence rates of AEs with the combination (Table 1-3 of protocol), a sample size of 81 evaluable subjects is estimated based on a two sided 95% confidence interval for an incidence rate of an AE using the large sample normal approximation that will extend 0.10 from the observed incidence rate of an AE (precision or margin of error of 10%) for an expected incidence rate of 30%.

Thus, with the estimated sample size of 90 subjects there is at least 90% probability to detect an AE with a true incidence rate of 2.5%. Considering drop-out rate of 10%, approximately 90 subjects will be enrolled for safety and efficacy assessment of this study.

Novartis has decided to permanently halt recruitment based on a re-evaluation of the development strategy for sabatolimab. Subjects who are currently on study treatment or in follow-up will be continue per the protocol. At the time of this amendment, 39 subjects have been enrolled into the study.

4 Change to protocol specified analyses

- [REDACTED]
- [REDACTED]
- No supportive/subgroup/sensitivity analysis performed due to MBG program closing/due to fewer sample size. Additionally it is mentioned in protocol that subgroup analysis may be performed. Hence it is agreed to not have these analysis.

5 Appendix

